  - *Methylprednisolone 500 mg IV over 30 minutes*
  - *Alemtuzumab 12 mg IV over 4 hours*
  - *Hourly temperature, pulse and blood pressure*
  - *First month (Day 6 – 30) – part of normal care*
  - *Valaciclovir 500 mg PO od*
  - *Bactrim DS (960 mg) PO 3 times per week (Mon, Weds, Fri)*
  - *Bloodwatch pathology tests (Every month) – part of normal care*
  - *FBC/lymphocyte subsets (4 ml) – lymphocyte subsets will be performed at weeks -1, 4, 9, 13, 26, 35, 50, 57, 61, 65, 78, 83 and 104.*
  - *EUC/LFTs (10 ml)*
  - *Urine red cell count*

[figure not shown]
- *Urine albumin*
- *UACR*
- *TSH (every 3rd month)*
- *Intervention visits (At weeks 10 and 30 provided B-cell count >30% of pre-treatment level.*
  - *Loratidine 10 mg PO 30 minutes prior to rituximab.*
  - *Methylprednisolone 100 mg IV over 30 minutes, commencing 30 minutes prior to rituximab.*
  - *Rituximab 100 mg per m^2 or placebo IV over 1 hour*
- *Monitoring visits (Every 6 months – weeks 25, 51, 77, 103, 129)*
  - *Review of relapse history*
  - *Review of adverse events*
  - *Review of intercurrent illness*
  - *Review of concomitant medications*
  - *EDSS*
  - *Monitoring visits may be conducted remotely via telehealth whether for reasons of COVID-lockdowns or remoteness of the participant*
- *MRI (Every 12 months – Baseline, Weeks 51, 103, 155)*
  - *MRI Brain*
  - *Closeout visit (Week 155 or earlier at close of study)*
  - *Review of relapse history*
  - *Review of adverse events*
  - *Review of intercurrent illness*
  - *Review of concomitant medications*
  - *EDSS*
  - *MSIS-29*
- *The timeline of participant involvement and total time commitment per patient in the trial is outlined in Table 3. Participants will also undergo the following procedures as part of normal care for someone receiving alemtuzumab. Admissions to day infusion centre for 8 hours on 5 days in year 1 and 3 days in year 2 for administration of alemtuzumab. They will also undergo monthly blood and urine tests as listed about through any private pathology firm convenient to them as part of the Bloodwatch® (RxMx®, Australia) monitoring program. The additional lymphocyte subset counts will be undertaken as part of the same blood draw and will not involve any additional tubes or time.*
- *Time constraint tolerance on study related procedures will be as follows:*
- *Screening visit, Enrolment, Review visit, EDSS and Screening bloods will be +/- 1 week.*

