**Figure 1. RAMBLE Trial Design**

Following screening participants will be randomized 2:1 to receive either rituximab or placebo at weeks 10 and 30 after each dose of alemtuzumab. Follow up will be for a minimum of 2 years and a maximum of 4 years. Alemtuzumab administered at Week 1 and Week 53 (yellow arrows). Rituximab/placebo administered at Weeks 10 and 30 in each of Years 1 and 2 (blue arrows). Clinic reviews at -4 and -1 weeks and then every 6 months (black arrows). MRI every year (red arrows).

---

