## **i. Outcome Measures**

- *Primary outcome measure: the frequency of autoimmune adverse events (autoimmune thyroid disease, idiopathic thrombocytopenia, anti-GBM renal disease and any other autoimmune diseases).*
- *Secondary outcome measures:*
  - *Other adverse events, in particular infections*
  - *Measures of alemtuzumab treatment efficacy*
    - *Time to first relapse or new disease activity on MRI*
    - *Time to first relapse*
    - *Annualised relapse rate*
    - *EDSS*
    - *MSIS-29*
    - *Sustained disability progression*
    - *Number of new T2 lesions on MRI*
    - *Number of new Gd-enhancing lesions on MRI*
  - *Measure of lymphocyte reconstitution*
    - *Total lymphocyte count*
    - *CD4, CD8, CD20 counts*
    - *B-cell subpopulation counts.*

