## **I. Data Analysis and Statistical Considerations**

- *The primary outcome measure for this study will be frequency of autoimmune adverse events. Because the duration of follow up will not be uniform for all participants and in order to make the maximal use of data the frequency of autoimmune adverse events will be modelled using a Cox Proportional Hazards time to event analysis (with onset of autoimmune adverse event as the event of interest). Although randomisation will be stratified for clinical site and sex, these factors as well as age and disease severity (MSSS) will be included in the model. Analysis will be performed on an intention-to-treat basis.*
- *Secondary outcome measures will be analysed as follows:*
  - *Other adverse events (MedDRA terms) will be compared using frequencies and chi-squared statistics.*

- 
- *Efficacy in terms of MS outcomes will be analysed using time to event analysis (Cox Proportional Hazards method) for annualized relapse rate and sustained disability progression (6 months), including the factors listed above for the primary outcome analysis in the model.*
  - *Other secondary outcomes (e.g. change in EDSS, new T2 and Gd-enhancing MR imaging lesions) at 1 and 2 years will be assessed using linear regression analysis provided assumptions are met (in which case non-parametric methods will be used).*
  - *Any effect of laboratory measures (lymphocyte subsets,) and baseline characteristics will be explored using regression analysis.*
  - *All statistical analyses will be conducted using STATA® v16 software (StatCorp®, US). The primary outcome of this trial will be met if the hazard ratio of autoimmune adverse events in the treatment (rituximab) arm is significantly lower than that seen in the placebo arm. The study is unlikely to have sufficient power to identify any significant differences in the frequency of other adverse events or MS disease outcome measures, but these will be looked at carefully to ensure that these outcomes are similar in the two groups.*

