#### Statistical power calculation

- *A previously published sample size calculation based on a Phase I study suggests that a trial of 80 participants (40 in each arm) would have 80% power with  $p < 0.05$  to detect a reduction in autoimmune adverse events from 40% down to 10%.*
- *Primary analysis will be based on observed data only but a sensitivity analysis where missing data is imputed using maximum likelihood imputation methods will be undertaken.*
- *All statistical analyses will be conducted by our in-house statisticians, [name] and A/[name].*

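### The protocol assigns a Cox time-to-event analysis to annualised relapse rate, which as written yields a hazard ratio for first relapse and not a relapse rate or rate ratio

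*Protocol*

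**What the plan says.** Section 3.i (Outcome Measures) lists eight measures of MS efficacy among the secondary outcomes, without ranking them. "Time to first relapse" and "Annualised relapse rate" are separate entries.

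The data analysis section of the protocol then gives the method for MS efficacy as a time-to-event analysis ("Cox Proportional Hazards method) for annualized relapse rate and sustained disability progression (6 months"), with the same covariates as the primary model. It names no method for time to first relapse, nor for time to first relapse or new MRI activity. The next item covers the remaining outcomes: "Other secondary outcomes (e.g. change in EDSS, new T2 and Gd-enhancing MR imaging lesions) at 1 and 2 years will be assessed using linear regression", with non-parametric methods as the alternative. No count model, person-time offset or recurrent-event form of the Cox model appears anywhere in the protocol.

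Two design facts bear on the point. The six-monthly monitoring visits and the closeout visit in section 3.h each include "Review of relapse history". Follow-up also differs between participants: "Follow up will be for a minimum of 2 years and a maximum of 4 years" (legend to Figure 1; the Timeline section gives 2.5 to 4.5 years).

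**The concern.** Annualised relapse rate is the number of relapses divided by the time observed. A participant with three relapses contributes three, and follow-up time is the denominator. The ordinary Cox model answers a different question: how the instantaneous risk of a first relapse compares between the arms. Its output is a hazard ratio, and a participant leaves the risk set once the event has occurred.

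The method has therefore been attached to the wrong one of two listed outcomes. Taken literally, annualised relapse rate has a method that cannot produce it. Taken charitably, the analysis is really of time to first relapse, and annualised relapse rate has no analysis.

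At stake is part of the check on the second hypothesis, that MS control is similar with rituximab and with placebo. The protocol concedes low power for MS outcomes but undertakes to examine them for similarity between arms. A hazard ratio reported as a comparison of relapse rates would be mislabelled, and it would use less of an already small body of relapse data.

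**Working it through.** **Plan's own figure.** There is none to reproduce. The protocol states no relapse rate, no dispersion and no power for relapse outcomes. Its sample size concerns autoimmune events and does not bear on this point.

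**Outcome against method.**

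| Outcome in section 3.i | Method named in the analysis section | Fit |
|---|---|---|
| Time to first relapse | none | Cox would fit |
| Time to first relapse or new MRI activity | none | Cox would fit |
| Annualised relapse rate | Cox | does not yield a rate |
| Sustained disability progression | Cox | fits, as time to progression |

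The item on other secondary outcomes does not fill the gap, because linear regression at 1 and 2 years does not suit a censored time to relapse. The only description of what the Cox model is fitted to is in the primary analysis: "time to event analysis (with onset of autoimmune adverse event as the event of interest". That is the ordinary first-event form.

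**Share of relapses left unused by a first-event analysis.** Assumed inputs: relapse rate r per year, constant and equal in all participants on average; follow-up T years; dispersion k (gamma frailty variance). The mean count is m = rT.

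- Probability of no relapse: P0 = exp(−m) if k = 0 (Poisson); P0 = (1 + km)^(−1/k) if k > 0 (negative binomial).
- First relapses per participant: 1 − P0.
- Share of relapses after the first: 1 − (1 − P0)/m.

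For T = 3 years:

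| r | m | k | 1 − P0 | Share after the first |
|---|---|---|---|---|
| 0.2 | 0.6 | 0 | 0.451 | 1 − 0.451/0.6 = 0.25 |
| 0.2 | 0.6 | 1 | 0.375 | 1 − 0.375/0.6 = 0.375 |
| 0.3 | 0.9 | 0 | 0.593 | 1 − 0.593/0.9 = 0.34 |
| 0.3 | 0.9 | 1 | 0.474 | 1 − 0.474/0.9 = 0.47 |

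With 80 participants, the expected totals are 80 × 0.6 = 48 and 80 × 0.9 = 72 relapses. The unused number runs from 48 × 0.25 = 12 to 72 × 0.474 = 34.

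Over a wider grid (r from 0.1 to 0.4, T from 2 to 4 years, k from 0 to 1), the share runs from 9% (r = 0.1, T = 2, k = 0) to 62% (r = 0.4, T = 4, k = 1).

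**Is the hazard ratio the rate ratio?** A simulation used a true rate ratio of 0.50, a control rate of 0.3 per year and follow-up uniform between 2 and 4 years, in 20,000 simulated participants. The first-event hazard ratio was 0.51 with k = 0 and 0.55 with k = 1. The first differs from 0.50 only by simulation error. The second is expected: with gamma frailty of variance 1, the first-event hazard ratio at time t is 0.5 × (1 + 0.3t)/(1 + 0.15t). This is 0.50 at t = 0, 0.5 × 1.6/1.3 = 0.62 at 2 years and 0.5 × 2.2/1.6 = 0.69 at 4 years. With heterogeneity between patients, the hazard ratio drifts towards 1 while the rate ratio stays at 0.50.

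**The case against.** The strongest reply is that the Cox family is wider than the first-event model. An Andersen-Gill form uses every relapse and gives a ratio of relapse intensities, and the protocol never says that relapses are to be analysed at first event only. This stands to the extent that the loss of later relapses follows from the ordinary model and is not stated in the text. It does not rescue the wording. No recurrent-event form or robust variance is mentioned, and the only use of Cox that the protocol describes is on event onset. If such a form was intended, the text must say so.

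Several stronger readings are tempting and go too far:

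- A reader might infer that participants who relapse repeatedly drop out of the analysis. They do not. Each still counts once, through the first relapse, and the later relapses remain on record from the visits.
- A reader might infer that annualised relapse rate is a main measure for the second hypothesis. The hypothesis names no measure and the outcome list does not rank them. Progression, EDSS and MRI lesions also speak to it and have named analyses.
- A reader might infer that the treatment comparison is badly biased. The share of relapses unused is not a bias. In the simulation the effect was mildly attenuated (0.55 against 0.50), not reversed.

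It might also be said that the detail belongs in the SAP, which is not at hand. But the protocol does not leave the method open. It names one and attaches it to the wrong outcome, so an SAP with a count model would depart from the protocol.

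**Conclusion.** Wrong as written, and of modest severity. The protocol lists two relapse outcomes, gives Cox to the one it does not fit, and names no method for the one it does. In its ordinary form the named analysis produces no relapse rate or rate ratio.

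The size depends on assumptions, because the protocol supplies neither a rate nor a dispersion: 25% to 47% of relapses unused at 0.2 to 0.3 per year over 3 years with dispersion 0 to 1, and 9% to 62% over the wider grid. The upper part of either range needs marked heterogeneity between patients and should not be quoted alone.

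This is not a defect that threatens the trial. The outcome is secondary, the protocol says that power for MS outcomes is unlikely to be sufficient, and success is defined only by the hazard ratio for autoimmune events. No sample size or success criterion rests on annualised relapse rate.

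**What to change.** Amend the sentence on MS efficacy in the data analysis section:

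- Assign Cox regression to time to first relapse, time to first relapse or new MRI activity, and time to sustained disability progression.
- Analyse annualised relapse rate with a count model of the number of relapses, with log follow-up time as offset, and report a rate ratio with 95% CI. Negative binomial regression is one choice, and Poisson regression with robust standard errors is another. Nothing in the protocol makes one clearly better with 80 participants.
- If a recurrent-event Cox model was intended instead, name it and its variance estimator, and describe its result as a ratio of relapse intensities.

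The cost is one sentence. The relapse data are already collected at the scheduled visits, the offset deals with unequal follow-up, and no new software, visit or participant is needed.

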#### **d. Recruitment/ Selection**

- *Potential participants will be recruited through the MS or CNS inflammatory disease clinics of the six participating hospitals with a cap of 20 participants at any single centre. Participants will not be financially compensated for their involvement in this trial but will be reimbursed for any reasonable costs of participation (e.g. parking costs).*
- *Participants will be recruited by neurologists at each site, who having identified a patient who is about to commence treatment with alemtuzumab, will invite the pwMS to participate in the trial. Potential participants will be provided with an introduction and overview of the study by their treating neurologist. Those who are interested in participating will be provided with the Patient Information and Consent Form (PICF) to take away and read and a further visit with one of the study investigators will be arranged at a later date.*
- *Participants will be enrolled in the study at the baseline/screening visit provided they:*
  - 1. *Have given written informed consent*
  - 2. *Meet all the inclusion criteria*
  - 3. *Meet none of the exclusion criteria*
- *Randomisation: Participants will be randomised at enrolment to treatment with rituximab or placebo at a 2:1 ratio. Randomisation will be performed using the randomisation module of the REDCap database based on a random number sequence produced in Excel®, Microsoft (Seattle, CA, USA) stratified by site, sex and age. This randomization sheet will be generated by Assoc/[name]. There will a cap of 20 participants for any single site.*
- *Blinding and allocation concealment: This will be a double-blinded study with both patient and treating physician blinded as to whether the participant is receiving active treatment or placebo. At the screening visit, participants will be assigned a unique participant Screening Number. At the baseline/enrolment visit, after eligibility is confirmed and the full consent form has been signed, a Participant Identification Number (PIDN) will be assigned. PIDNs will be randomly assigned to intervention or placebo groups according to the randomisation code provided by the randomisation sheet. Randomisation*

---

codes will only be visible through REDCap to site pharmacists who will make up the active treatment and placebo. Both rituximab and 0.9% sodium chloride (placebo) are colourless fluids, so will be indistinguishable to treating physician, participants and other staff.

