  - *At the conclusion of the trial, the Principal Investigator or nominee will perform a final inventory. If any supplies cannot be accounted for, this will be documented on the product accountability form together with an explanation of the discrepancy. The originals of the product accountability and dispensing logs must be sent to the trial coordinator. The Principal Investigator will retain copies of these logs on file.*
  - *Retention of Samples*
  - *The Principal Investigator or delegate will maintain accurate records demonstrating dates and amount of product received, to whom dispensed and accounts of any product accidentally or deliberately destroyed. It will be the responsibility of the Principal Investigator or delegate to ensure that adequate samples of all trial doses are retained in accordance with the relevant regulatory guidelines. For example, for trials conducted under the CTN scheme in Australia, at least a sample from each batch of product used in the trial should be retained for one year longer than the shelf-life of the product, and to comply with ICH-GCP requirements, sufficient quantities of the product(s)*

---

*should be retained either until the analyses of the trial data are complete or as required by the applicable regulatory requirements, whichever represents the longer retention period.*

- *Study Procedures and Visits*
- *Participants will be required to undergo the following study procedures and visits.*
- *Screening Visit (-30 - -7 days)*
  - *Informed consent will be obtained*
  - *Completion of eligibility criteria checklist*
  - *Comprehensive review of medical history including; details of MS history, other past medical and surgical history, past and current medications, family history, social history and allergies*
  - *Comprehensive medical and neurological examination*
  - *EDSS*
  - *HADS*
  - *Baseline/enrolment Visit (-7 - -4 days)*
  - *Informed consent will be re-obtained*
  - *Review of neurological symptoms*
  - *Review of medications*
  - *EDSS*
  - *MSIS29*
  - *Blood tests – FBC, EUC, LFT, TFT, Lymphocyte subsets, bHCG (in women)*
  - *Urine screen – red cell count and albumin*
  - *UACR*
- *Alemtuzumab therapy visits (Year 1, Day 1 – 5; Year 2, Day 1-3) – part of normal care*
  - *Loratidine 10 PO od (continued for 10 days)*
  - *Valaciclovir 500 mg PO od*
  - *Bactrim DS (960 mg) PO 3 times per week (Mon, Weds, Fri)*
  - *0.9% Sodium Chloride IV 1L over 8 hours*

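### The regressions of EDSS change and new MRI lesions name no covariate, and no listed model contains baseline EDSS: a modest, avoidable loss of precision

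*Protocol*

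**What the plan says.** All of the analysis text is in section 3 of the Protocol, under Data Analysis and Statistical Considerations.

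- **Primary Cox model.** After naming site and sex, it says that "these factors as well as age and disease severity (MSSS) will be included in the model".
- **Cox models for relapse and sustained progression.** The same set is carried over: "including the factors listed above for the primary outcome analysis in the model".
- **Other secondary outcomes.** The text reads "change in EDSS, new T2 and Gd-enhancing MR imaging lesions) at 1 and 2 years will be assessed using linear regression analysis". It gives outcome, time points and method, but no covariate.
- **Exploratory item.** Laboratory measures and "baseline characteristics will be explored using regression analysis". This does not place them in the comparison of arms.
- **Power.** For other adverse events and MS outcomes: "The study is unlikely to have sufficient power to identify any significant differences".

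Elsewhere, the Recruitment/Selection section has randomisation "stratified by site, sex and age". The list of study procedures and visits, and Table 3, place an EDSS at screening and another at the enrolment visit. A pre-treatment scan is also scheduled: "MRI (Every 12 months – Baseline, Weeks 51, 103, 155".

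**The concern.** The Protocol lists covariates model by model and stops doing so at the outcome where baseline disability bears most directly. MSSS, which the reference list describes as rating severity from disability and disease duration, enters the relapse and progression models. Nothing comparable is named for change in EDSS.

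A change score does use the baseline, but only by subtraction, which fixes the baseline slope at 1. If follow-up EDSS regresses on baseline with a slope below 1, subtraction over-corrects and leaves avoidable noise in the arm contrast.

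The second hypothesis is that MS control is similar in the two arms, and the Protocol already concedes low power for MS outcomes. Where the aim is to show similarity, a noisier contrast is not harmless: it makes a non-significant difference more likely and says less about how large a difference could have been missed.

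**Working it through.** **Plan's own figure.** There is none on this point. The only power calculation concerns autoimmune events (80 participants, 40% against 10%) and is not an input here.

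**Inputs.**
- 80 participants randomised 2:1 (Protocol, section 3, Methodological Approach), so about 53 and 27. The power paragraph speaks of 40 in each arm; the variance ratio below does not depend on the split.
- r, the correlation between baseline and follow-up EDSS: **assumed**, 0.5 to 0.9. The Protocol gives neither r nor an SD.
- Equal variance s² at baseline and follow-up: **assumed**.

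**Step 1: variance of the arm contrast.** Put k = 1/53 + 1/27 = 0.0559, so √k = 0.236.
- Unadjusted change: 2(1−r)·s²·k
- Adjusted for baseline: (1−r²)·s²·k
- Ratio: (1−r²) / [2(1−r)] = (1+r)/2

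Once baseline is in the model, the arm contrast is the same whether the outcome is change or the follow-up score.

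**Step 2: size.** The SE reduction is 1 − √((1+r)/2). The equivalent extra sample is 2/(1+r) − 1.

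| assumed r | variance ratio | SE reduction | equivalent extra participants |
|---|---|---|---|
| 0.5 | 0.75 | 13% | 33% |
| 0.7 | 0.85 | 8% | 18% |
| 0.8 | 0.90 | 5% | 11% |
| 0.9 | 0.95 | 2.5% | 5% |

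**Step 3: illustration in power.** For an assumed difference of 0.5 SD with 27 against 53 (two-sided 5%, normal approximation), adjustment moves power from 56% to 69% at r = 0.5, from 78% to 84% at 0.7, and from 92% to 94% at 0.8.

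**Step 4: is chance imbalance an extra harm?** The baseline difference between arms has an SD of 0.236 baseline SDs. A fraction (1−r) of it passes into the unadjusted change contrast, so its variance contribution is (1−r)²·s²·k. The two variances in Step 1 differ by

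2(1−r) − (1−r²) = 1 − 2r + r² = (1−r)²

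in the same units. The imbalance is therefore exactly the gap already counted in Step 2.

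**Step 5: MRI.** A count of new lesions has no baseline value of the same variable, so (1+r)/2 does not apply. A baseline lesion measure with correlation c to the outcome cuts the SE by 1 − √(1−c²): 0.5% at c = 0.1, 5% at 0.3 and 13% at 0.5, with c again assumed.

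**The case against.** **The text is silent on covariates; it does not exclude them.** A reader might infer that the Protocol prescribes unadjusted models. It does not say so, and covariates for a group of other secondary outcomes are often settled in a statistical analysis plan, which is not at hand. This stands, and it limits the point to what the sentence names. What remains is the contrast with the preceding item, which does name its covariates, and the absence of baseline EDSS from every listed model.

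**No bias.** A reader might infer that chance imbalance or regression to the mean distorts the arm comparison. Under randomisation neither biases the change contrast, and Step 4 shows that the imbalance is already inside its variance. This stands in full.

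**The gain may be small.** At r of 0.7 to 0.9 the SE falls by only 2.5% to 8%. This also stands.

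**Covariates are not free.** Six sites (5 terms), sex, age and baseline make 8 terms. If none were prognostic or balanced by design, the variance would inflate by about (80−3)/(80−8−3) = 77/69 = 1.12, enough to cancel the gain at r of 0.8 or more (0.90 × 1.12 ≈ 1.0). That is a pessimistic case, because randomisation is stratified on three of these factors. Baseline EDSS alone costs about 77/76 = 1.01, which leaves a net gain even at r = 0.9 (0.95 × 1.01 ≈ 0.96).

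**Little rides on it.** Trial success is defined on the autoimmune hazard ratio, and relapse and progression are analysed with MSSS in the model. This supports a low severity.

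**Conclusion.** The point holds as a modest efficiency improvement, mainly for EDSS. If the regression is fitted with only what the Protocol names, its standard error is larger than it need be: baseline adjustment would lower it by about 13% at r = 0.5, falling to 2.5% at r = 0.9. These figures rest on an assumed r, equal variances and a large-sample formula.

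A reader might go on to infer that the efficacy result is biased, or that the MRI comparison loses as much. The documents support neither. Allocation is random, and new-lesion counts are not change scores with a slope fixed at 1. Severity is minor: a secondary outcome, with low power already acknowledged.

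**What to change.** In Data Analysis and Statistical Considerations, add to the item on other secondary outcomes that:

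- the EDSS regressions at 1 and 2 years include baseline EDSS together with site, sex and age, which are the randomisation factors and are already in the Cox models;
- the regressions of new T2 and Gd-enhancing lesions include the same three factors and, optionally, the corresponding baseline lesion measure.

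State which pre-treatment EDSS serves as baseline (the enrolment score or the mean of the two). Either is defensible if fixed in advance. If a non-parametric method is used instead, say how baseline enters it, since a covariate does not carry over directly.

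The cost is one or two sentences, with no new data or visits. The small downside is the degrees of freedom spent on site in a model of 80. If sites recruit very unevenly, a pre-stated rule for pooling small sites would limit it.

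### The fallback rule for EDSS change and new MRI lesions names two conflicting methods if assumptions hold and none if they fail

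*Protocol*

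**What the plan says.** Protocol section 3, Data Analysis and Statistical Considerations, covers "Other secondary outcomes (e.g. change in EDSS, new T2 and Gd-enhancing MR imaging lesions) at 1 and 2 years". It assigns them "linear regression analysis provided assumptions are met (in which case non-parametric methods will be used"). Nothing else in the protocol restates or corrects this rule.

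The Outcome Measures section lists the two MRI outcomes as counts: "Number of new T2 lesions on MRI" and "Number of new Gd-enhancing lesions on MRI".

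The data analysis section also says of these outcomes: "The study is unlikely to have sufficient power to identify any significant differences in the frequency of other adverse events or MS disease outcome measures". It adds that they will still be examined to see that the arms are alike. The second hypothesis in section 2.b is that MS control is similar with rituximab and with placebo.

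**The concern.** The fallback is attached to the wrong condition. A statistician who follows the sentence literally has no single instruction if the linear-model assumptions hold and no instruction at all if they fail. An analysis plan that inherits the wording inherits the problem.

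The silent branch is probably the one that would be needed. New lesion counts after a therapy that the Background calls highly effective are likely to be mostly zero, so normal-error assumptions would be hard to defend. Even with the parenthesis repaired, linear regression stays the default for these counts, and the choice of method depends on inspecting the data.

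The protocol concedes low power here, so these outcomes will be read mainly through estimates and intervals. That makes a fixed model with an interpretable effect measure worth having.

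**Working it through.** **Reading the rule branch by branch**

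| Condition | Main clause | Parenthesis | Result |
|---|---|---|---|
| Assumptions met | linear regression | non-parametric methods | two conflicting methods |
| Assumptions not met | nothing | nothing | no method named |

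The only antecedent available to the parenthesis is that assumptions are met. There is no stated figure to reproduce.

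**How sparse the counts might be**

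The protocol gives no lesion rates, so these are assumptions: negative binomial counts with mean m and dispersion a (variance m + a·m²). The probability of no lesion is (1 + a·m)^(−1/a).

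- m = 0.3, a = 3: 1.9^(−1/3) = 0.81
- m = 0.2, a = 5: 2.0^(−1/5) = 0.87
- m = 0.5, a = 3: 2.5^(−1/3) = 0.74

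Arm sizes follow from the recruitment section: "Participants will be randomised at enrolment to treatment with rituximab or placebo at a 2:1 ratio". With 80 participants, 80 × 2/3 ≈ 53 receive rituximab and 27 placebo. Placebo participants with any new lesion would number about 27 × 0.19 = 5.1, 27 × 0.13 = 3.5 and 27 × 0.26 = 7.0.

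**Does the linear model mislead on false positives?**

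Null simulation, 27 vs 53, 10,000 runs per setting, means 0.1 to 3 and negative binomial size parameter k = 1/a of 0.3 to 0.5:

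- linear two-group test: type I error 3.9% to 4.8%
- Mann-Whitney test: 3.6% to 5.2%

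Neither shows material inflation at the nominal 5%.

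**Does a count model gain anything?**

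Simulation of 1,500 trials per setting, 27 placebo vs 53 rituximab, unadjusted, two-sided 5%. The table gives the share of trials with p < 0.05 for the linear test and for the negative binomial likelihood-ratio test.

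| Placebo mean | Rituximab mean | a | Linear | Negative binomial |
|---|---|---|---|---|
| 0.3 | 0.3 | 3 | 4.6% | 5.5% |
| 0.2 | 0.2 | 5 | 4.1% | 7.5% |
| 0.5 | 0.5 | 3 | 3.9% | 5.1% |
| 0.3 | 0.9 | 3 | 33% | 51% |
| 0.5 | 1.5 | 3 | 39% | 59% |
| 0.9 | 0.3 | 3 | 54% | 53% |
| 0.5 | 0.1 | 3 | 67% | 67% |

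The simulation standard error is about 0.6 percentage points near 5% and 1.3 near 50%. A separate run under assumed rates gave 53% against 34% with the rituximab arm worse, in line with the fourth row. The count model is more powerful when the rituximab arm does worse, the direction of concern for loss of MS control, and about equal when it does better. In the sparsest setting its likelihood-ratio test is somewhat liberal.

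**What the count model costs**

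In the sparsest setting (m = 0.2, a = 5), about 3.5% of simulated trials had an arm with no lesions and about 3% more failed to converge. Across the three null settings, the median ratio of upper to lower limit of the rate-ratio interval was 8 to 19.

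**The case against.** The best defence is that this is a slip of the pen whose meaning is obvious, in outcomes the protocol itself calls underpowered, with trial success resting only on the autoimmune hazard ratio. The exact model, the assumption check and the choice of non-parametric method are commonly left to an analysis plan, which may exist. Making linear regression conditional already shows awareness that the data may not suit it. A negative binomial model also has convergence problems and wide intervals when few participants have lesions.

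Most of that stands as a limit on importance. It does not remove the error: the protocol chose to state the rule, and the stated rule cannot be followed.

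Three stronger readings are tempting but not supported:

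- **That the rule picks the wrong method in both branches.** The text never assigns linear regression to the case where assumptions fail. It is contradictory in one branch and silent in the other, not cleanly inverted.
- **That the linear analysis would give impossible negative lesion counts.** Under the assumed rates, a linear-model interval for the placebo mean falls below zero in 34% to 63% of simulated trials. But the treatment comparison is a difference between arms, which may properly be negative, so that figure does not measure the planned comparison.
- **That false positives are inflated.** The simulations show otherwise.

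Nor is it fair to say that non-parametric methods cannot give an effect estimate or adjust for covariates. The protocol names no particular method, and some do both.

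**Conclusion.** The point holds as a minor one. The rule for EDSS change and new lesions is misstated and needs correcting. That conclusion rests on the text alone and on no numerical assumption.

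The case for a count model is a recommendation, and it depends on assumed lesion rates (means of 0.2 to 0.5 on placebo with strong overdispersion). Its benefits are a rate ratio that speaks to the similar-efficacy hypothesis and, if the rituximab arm were three times worse, power of about half rather than about a third. It brings no improvement in type I error, and with very sparse counts control can be slightly worse.

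The primary analysis and its sample size are not touched.

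**What to change.** At minimum, reword the parenthesis so that non-parametric methods apply otherwise, that is, when the assumptions are not met.

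Better, remove the data-dependent choice:

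- **New T2 and Gd-enhancing lesions:** pre-specify negative binomial regression, reporting a rate ratio with 95% CI and a likelihood-ratio test. Name an exact or rank-based fallback for when an arm has no lesions or the model does not converge.
- **Change in EDSS:** pre-specify one model adjusted for baseline EDSS. Study Procedure records EDSS at both screening and enrolment, so state which value is the baseline.

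The cost is a wording amendment, with no new data, visits or participants. The trade-off is occasional non-convergence and wide intervals if lesions are rare. The change should be made before unblinding.
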